#### **D.7.a Analyses to Test Specific Aims:**

The **primary specific aim** of this project is to examine if GCBT produces significant reductions in PTSD relative to the *SGP* condition and to determine if these changes are durable across a 12 -month follow-up interval. Two hypotheses will be tested.

**Hypothesis 1.** Patients with PTSD who receive GCBT will show greater reductions in PTSD-related symptoms relative to patients who receive *SGP*, at post-treatment assessment, a between-group difference that will persist through 6 month follow-up. To test this hypothesis, we will use multilevel latent growth modeling. Whereas a traditional latent growth model approach would suffice in many instances (e.g., when patients are treated individually), as noted earlier, the delivery of treatment in group format is likely to result in the violation of the assumption of independent observations (i.e., within-group similarity on treatment outcomes and process variables; cf. Schnurr et al., 2001, 2003). In initial analyses, we will evaluate the

extent of dependency (i.e., clustering) by calculation of intraclass correlations (ICCs) using variance estimates from unconditional cell means models of key outcome variables (cluster = treatment group). Our proposed  $N$  of 196 will be clustered into 14 treatment groups per condition. Assuming non-zero ICCs, a multilevel approach will be incorporated into the latent growth framework in order to obtain correct standard errors, test statistics, and confidence intervals. In the traditional multilevel modeling, the design would be construed as a three-level model; i.e., repeated observations (Level 1) nested under individuals (Level 2), individuals nested under treatment groups (Level 3). However, because the first two levels are combined in the multivariate framework of latent growth modeling, this design can be characterized as a two-level model (i.e., latent growth factors are nested under treatment groups) where time-invariant covariates (i.e., dummy codes for treatment condition) are included to account for the within-group and between-group variability in initial status (pre-treatment) and symptom change (improvement over active treatment and follow-up). In the latent growth model portion of the models, the intercept will be centered on pre-treatment (i.e., first slope loading will be fixed to 0.0). Because there is no substantive interest in the form of the growth trajectory, intermittent time points (i.e., slope factor loadings) will be freely estimated and the final timepoint of interest (e.g., post-treatment) will have a corresponding factor loading fixed to 1.0. Accordingly, the mean and variance of the slope will convey the fixed (average) and random effects (individual differences) of change for the given time interval of interest. The Level 2 variables of treatment condition (single dummy code using *SGP* as reference group) will be included as predictors to account for individual differences in treatment response and variability in outcome across treatment groups. To examine pre-treatment differences between treatment conditions, the intercept (centered on pre-treatment) will be regressed onto the treatment covariates (i.e., significant paths are indicative of differences in pre-treatment levels as a function of treatment condition). Any pre-treatment differences will be accommodated into the interpretation of findings and in the parameterization of the models (e.g., regression of the slope onto the intercept, as well as covariates such as treatment condition). The dependent variable for this analysis is the CAPS total score. Additionally, PCL will be examined, using the same analytic approach, in order to examine respondent effects (interviewer-rated versus self-report).

***Hypothesis 2.*** Reductions in PTSD symptom severity will be maintained in the GCBT group at 12-month follow-up. Much as with Hypothesis 1, multilevel latent growth modeling will be used. In the analyses to examine Hypothesis 2, we will not include the treatment condition covariate but will include the site dummy code, to examine potential site differences. To test the prediction that the means of 6mos and 12mos do not differ, the slope factor loadings corresponding to these two time points will be constrained to equality and compared to the fit of a latent growth model where the 6 mo time point was freely estimated ( e.g., Baseline model:  $0^{* * 1}$ ; hypothesized model:  $0^{* * 1} 1$ ).

The **secondary aim** is to examine the generalizing effects of both GCBT and *SGP* on co-morbid conditions, distress and impairment. Because most trials in the PTSD literature do not include a thorough assessment of treatment generalization, it is unknown whether available treatments only address PTSD or whether gains generalize to related domains of functioning, including co-

morbid conditions such as depression, generalized anxiety, and alcohol use. Three hypotheses are proposed:

**Hypothesis 3.** For patients who are diagnosed with co-morbid Major Depressive Disorder (MDD), Generalized Anxiety Disorder (GAD), and/or Alcohol abuse prior to treatment, GCBT will produce significantly larger symptom reductions for these conditions, relative to SGP at post-treatment assessment and these generalized changes will show stability at 6 mo follow-up (FU). To test this hypothesis, we will use multi-level analysis, as discussed for Hypothesis 1. For continuous variables (BAI, BDI-II, SIP), we will use the same approach as described for Hypothesis 1. Although latent growth modeling can accommodate categorical outcomes (e.g., MDD+, MDD-) with an appropriate estimator (e.g., robust weighted least squares, maximum likelihood with numerical integration), there is concern about the estimation failure resulting from low cell frequencies, particularly at post-treatment and follow-up. In the event that cell frequencies are too low, we will augment the analyses from the continuous variables with more descriptively oriented statistics showing the rates of comorbidity decline at each assessment point as a function of treatment condition.

**Hypothesis 4.** Patients who receive GCBT will report less distress and impairment, relative to patients who receive SGP, at post-treatment assessment, a between-group difference that will persist through 6 month follow-up. To test this hypothesis, we will use multi-level analysis, as discussed for Hypothesis 1. For continuous variables (SF-36 subscales), we will use the same approach as described for Hypothesis 1.

**Hypothesis 5.** Gains in these domains (distress and impairment) will be maintained in the GCBT group at 12-month follow-up. To test this hypothesis, we will use multilevel latent growth modeling, using the same approach as discussed for Hypothesis 2.

**D.7.d. Secondary data analyses:** In addition to analyses designed to test these hypotheses, several secondary analyses will be conducted. **(1). Diagnostic and reliable change status:** In order to facilitate comparison with other RCTs, we will compute the percentage diagnosed with PTSD for both GCBT and SGP at post-treatment and , 3- and 6- mo follow-up. To determine reliable change, we will follow guidelines outlined by Jacobson and Truax (1991). Specifically, the reliable change index utilizes both the reliability of measurement device, along with a confidence interval, to determine reliable change. We will utilize CAPS Total scores and a stringent confidence interval (95%) to determine reliable change scores within both the GCBT and SGP conditions, at post-treatment and 6 mo follow-up assessment.

**(2). Examine the generalizing effects of both GCBT and SGP on healthcare utilization.** We will examine the effect of PTSD group treatment on healthcare utilization. We expect that veterans who receive GCBT will display less health care utilization relative to veterans who receive SGP. We will use the same multilevel analysis approach described above (with number of health care visits as the continuous variable).

**(3). Predictors of individual differences in outcome:** Although the primary aims of this RCT do not include a focus on individual differences that may affect outcome, we propose analyses to look at select variables in this regard. Recognizing that these are exploratory, we propose to look at (1) the number of sessions attended, (2) group psychotherapy alliance (four

subscales of the CALPAS), (3) treatment credibility, and (4) homework compliance, defined as the percentage of homework that the veteran completes, as well as the quality of that homework as rated by the therapists. For analyses involving the number of sessions attended, group alliance, and treatment credibility, we will use data from both the GCBT and *SGP* conditions.

Number of sessions attended will range from 1-14 for patients in both conditions. For group psychotherapy alliance, the CALPAS will be used. For treatment credibility, the four items from the treatment credibility measure (administered following session 1) will be summed to form a composite score. These analyses will examine the direct and moderating effects of each of these variables on variation in treatment response using the CAPS Total score as the outcome. The same multilevel latent growth modeling approach described earlier will be used, bringing these variables into the analysis as additional predictors of within (individual) and between group (treatment groups) variability in symptom change. Of particular interest will be the possibility of significant interactions between each variable and treatment condition (e.g., a significant Treatment Condition x Alliance product term), which would indicate that the strength of effect of these variables on treatment outcome differs between the GCBT and *SGP* conditions (e.g., group alliance is more strongly related to treatment response in the *SGP* condition than the GCBT condition).

To examine the role of homework compliance, two composite variables will be formed: compliance between pre-and mid-treatment and compliance between mid-and post-treatment. The level of homework compliance may vary across the active treatment phase, and thus this variable will be treated as a time-varying covariate in the growth models. Specifically, it is expected that the mid- and post-treatment homework compliance variables will account for significant variance in the CAPS total score indicators that is unexplained by the underlying growth factors (i.e., latent intercept and slope) for the GCBT condition only. The same multilevel latent growth modeling approach described earlier will be employed, bringing these variables into the analysis as additional predictors of within (individual) and between group (treatment groups) variability in symptom change. Of particular interest will be the possibility of significant interactions between each variable and treatment condition, which would indicate that the strength of effect of these variables on treatment outcome differs between the GCBT and *SGP* conditions.

Treatment satisfaction data will not be examined analytically but will be used to determine consumer response in the event that GCBT has documented efficacy and is targeted for broad-scale dissemination.

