**Rationale for a multi-site study:** The involvement of multiple sites is required for several reasons. First, given the study sample, two VA medical centers are required in order to enroll a sufficiently large sample to test our primary hypotheses. The VA Boston/National Center for PTSD ([name], PI) and the VA Providence ([name], PI) are supportive environments for this RCT, with considerable experience in clinical trial research. Data collection will occur at these two sites. In addition to accruing a sufficiently large sample, inclusion of two data collection sites will facilitate better representation of racial and ethnic minorities. Second, the developer of GCBT is located at the University of Memphis ([name], Co-I) and is integral to the success of this project.

**Between-site coordination/communication:** Communication is an essential component of between-site coordination. We will follow rigorous, specified procedures for training, certification, and monitoring of all staff. The Boston site will enroll 112 and the Providence site will enroll 84 male veterans with PTSD, using the same recruitment and screening procedures, identical inclusion and exclusion criteria, standardized administration of semi- structured interview measures and self-report questionnaires, and manual-driven therapy procedures. Data entry at both sites will include double-entry procedures, to ensure accuracy, and standardized software which will detect and flag aberrations in data entry. This software will

also track scheduled visits, permitting careful patient tracking during the follow-up interval. The software will reside on a secured server, behind the VA firewall, accessible only to personnel of the study. We will follow state-of-the-art practices for the design and conduct of a multi-site study, with two recruiting sites following identical protocols, a Steering Committee (Drs. [name], [name] and [name]) that is in frequent (i.e., weekly) contact with one another, consistent statistical support throughout the duration of the trial, and a data safety and monitoring board that is in close contact with the trial. Minutes will be maintained for each conference call, to facilitate between-site coordination.

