**D. 3. Procedures for conducting RCT: GCBT versus SGP**

**Recruitment and management of participants:** One of the difficulties in conducting a study of any group treatment is that participants who have enrolled in the study must wait until

a sufficient number of participants have collected to form a cohort. We proposed two approaches to manage this difficulty. First, recruitment will occur in “waves,” meaning that there will be 1-month intervals (every 3-4 months) where referrals will actively be sought. During these waves, efforts to screen and assess potential participants will be maximized, to concentrate resources on the formation of a cohort (14 participants). During the recruitment process, each participant will be made aware of the research requirements and have a chance to decline participation. Second, the project coordinator, with assistance from [name], will work with each participant as soon as he is enrolled in the study. The project coordinator will provide interim clinical care and remain in close contact with the participant while he is waiting for treatment to begin. As reported by Schnurr et al. (2001), this approach appeared successful in reducing attrition from the Cooperative 420 study, as only 3.7% of their PTSD veteran participants dropped out prior to randomization. As discussed in Section D.1, we will recruit 280 potential participants, for a final  $n$  of 196 to begin the trial (70% enrollment). Recruitment will occur in 7 waves (Year 01-1 wave, Year 02: 2 waves, Year 03: 2 waves, Year 04: 2 waves; Year 05: 0 waves); each wave will include 14 enrolled Veterans (20 to be screened to reach this target). The project coordinator will maintain close contact with each veteran throughout each step of the study.

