**Is this RCT adequately statistically powered?** In the study design, several factors were involved in determination of sample size. **First**, we drew estimated effect sizes from the **two** pilot studies on GCBT and from a recent meta-analysis (Bradley et al., 2005). Within the MVA pilot study, which contrasted GCBT with a minimal contact comparison condition, effect sizes for PTSD measures ranged from .83 to 1.04 (Hedges's unbiased  $g$ , Hedges, 1981). Within our Vietnam veteran pilot data, the pre-post treatment effect size for the PCL-M was  $d = 1.43$ . Consulting the larger literature, Bradley et al. (2005) computed average effect sizes (Cohen's  $d$ ) of .84 for contrasts between CBT versus supportive therapy conditions and 1.01 for contrasts between ET + cognitive therapy versus supportive therapy conditions. However, in RCTs involving veterans, effect sizes tend to be smaller, owing to the chronicity and severity of combat-related PTSD in this population. In computation of sample size for this trial, we have selected a relatively low value of  $d$  (.50); review of available studies (including our own pilot data) suggests effect sizes ranging from 0.84 to 1.43. Recognizing that effect sizes for contrasts between CBT and supportive psychotherapy tend to average  $d = .84$  (Bradley et al., 2005), that data from samples with chronic PTSD tend to have smaller effects, relative to less severe samples, and that effect sizes drawn from relatively small samples can be unstable, we took a conservative stance in estimating the effect size for the GCBT versus SGP contrast to arrive at  $d = .50$ . **Second**, because treatment within both conditions of this RCT will occur in groups, the analytic plan must account for the cluster effect owing to the correlation of outcomes within groups (expressed as  $\rho$ , the intraclass correlation coefficient). There is one clustered variable in this design (individuals within groups) which will be adjusted for in determining sample size. Following guidelines provided by Hsieh (1988) and Diggle et al. (2002), we used an inflation factor that was driven by the  $\rho$  values from the MVA-related PTSD pilot data. In particular, the  $\rho$  estimate of 0.11 is a conservative assumption, based on the largest value obtained in the pilot MVA study. In the pilot MVA study ([name] et al., 2009), the  $\rho$  for the CAPS was 0.07, the  $\rho$  for the BDI-II was 0.03, and for the BAI, the  $\rho$  was 0.08. Within the Collaborative 420 study (Schnurr

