
et al., 2003), the  $\rho$  for the CAPS was 0.05. Thus, use of  $\rho = 0.11$  in our power calculations is a conservative assumption. Larger values of the  $\rho$  can occur when the outcome measures (among patients) have a concrete connection to one another. In studies of physician behavior within a clinic, the  $\rho$  values are larger when the physician directly contributes to the assessment of the patient outcome measures. For example, Stedman et al. (2008) analyzed two such studies, one study of patients within selected clinics who were followed to determine if their clinic physician did or did not provide osteoporosis management, and a second study of patients within clinics to determine if physician education induced physicians to improve the quality of osteoporosis management. In each study the  $\rho = 0.12$ . The outcome measure for the patient was the level of disease management delivered by the physician, an outcome directly determined by the physician. In contrast, for our proposed study, the person who assesses patient outcomes should have little or no effect on the values of the patient measure outcome. In our study, the  $\rho$  captures a subtler effect, namely, potential assessor bias, a much smaller effect than the effect of physician practice patterns. With a proposed group size of 7, a maximum  $\rho$  of 0.11, and  $d = 0.50$ , we estimated a total  $n$  of 196, using  $p < .05$ . Although only two of 14 outcome variables in the pilot study exceeded  $\rho > .10$  (see [name] et al., 2009), we felt it was preferable to be conservative regarding  $\rho$  levels in our power computations. **Third**, in computation of sample size, we relied on .80 power level, as is customary in power calculations for RCTs. Using these parameters, the total desired  $n$  will be 196 ( $n = 98$  per condition); each treatment group will begin with 7 men. Thus, based on previous studies on Group CBT, as well as current data regarding ICC in the context of clinical trials, we have been appropriately conservative in our power calculations.

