In addition to statistical significance, we were concerned about the potential clinical significance of these data. Presently, there is no agreed-upon effect size that is thought to be clinically significant. This is difficult to determine because effect sizes hinge on many variables (e.g., the size and nature of the sample, the amount of variance in the assessment strategy, the amount of variance in treatment administration). In our power calculations, we have relied on a .80 power level, to have a sufficient sample size for this RCT for statistical significance. Unfortunately, there is no consensus in the treatment literature regarding what constitutes a clinically significant effect size; Friedman and colleagues (2006) suggest that clinically meaningful differences between 2 active treatments would be illustrated by an effect equal to or greater than .30 (Cohen's  $d$ ). Consultation with [name] (Project Statistician) thus indicates that the proposed  $n$  will be sufficient to determine whether GCBT produces clinically meaningful outcomes.

**Analytic approach:** Data from both sites will be combined prior to analyses. [name], the Project Statistician, will work in close collaboration with [name] to perform the analyses. Prior to testing hypotheses, the outcome data will be examined to assess if they meet the assumptions for the proposed statistics (Tabachnick & Fidell, 2001). If the assumptions are not met (e.g., the data depart from normality, multivariate outliers are present), appropriate data transformations will be used. Additionally, the GCBT and SGP groups will be examined for pre-treatment differences, to test for group equivalency. These analyses will involve a series of independent  $t$ -tests on each of the outcome measures as well as demographic variables. Pre-treatment differences between conditions will be incorporated into the models used to examine the primary hypotheses, as described below.

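### The Hypothesis 1, 3 and 4 arm comparisons pool two sites without a site term, so any site difference in symptom change is left in the error of the arm contrast and costs precision

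*Combined protocol and SAP*

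**What the plan says.** Under Analytic approach the plan states: "Data from both sites will be combined prior to analyses". For Hypothesis 1, section D.7.a describes a two-level latent growth model in which "time-invariant covariates (i.e., dummy codes for treatment condition) are included to account for the within-group and between-group variability in initial status" and in symptom change. It then specifies the Level 2 predictor as one dummy code for condition, with SGP as reference. Hypotheses 3 and 4 refer back to this approach for their continuous outcomes.

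Site appears in the modelling text under Hypothesis 2, the maintenance analysis: "we will not include the treatment condition covariate but will include the site dummy code, to examine potential site differences". Hypothesis 5 uses the Hypothesis 2 approach.

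The only other adjustment is conditional. Pre-treatment differences between conditions are to be tested and, if found, carried into the models.

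On the design, the Overview says: "The Boston site will enroll 112 and the Providence site will enroll 84 male veterans with PTSD". Section D.3 describes recruitment waves meant "to concentrate resources on the formation of a cohort (14 participants"), who are then randomised between the two group treatments, and has each group at each site run by two therapists. The power section adds that "each treatment group will begin with 7 men", and D.7.a counts 14 treatment groups per condition.

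**The concern.** The plan expects that the sites may differ and already has the variable, but uses it only where the arms are not compared. None of the stated hypothesis tests of GCBT against SGP allows for site.

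This matters because of how the groups appear to be formed. If each cohort yields one GCBT and one SGP group at the same site, site is balanced between the arms. A site difference in how much men improve then cancels out of the arm difference but remains in the spread of group results within each arm. That spread is the error term for the arm contrast. At stake is precision in a trial with 28 clusters and no spare power.

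The conditional adjustment would not be expected to help. It is triggered by differences between conditions, and a factor balanced across conditions will not normally show one.

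**Working it through.** **Inputs from the documents.** d = 0.50, which the power section describes by saying "we took a conservative stance in estimating the effect size for the GCBT versus SGP contrast"; intraclass correlation (rho) 0.11, of which it says the "estimate of 0.11 is a conservative assumption, based on the largest value obtained in the pilot MVA study"; groups of 7; 14 groups per arm; p < .05 (sidedness not stated, two-sided taken here); power .80; site targets 112 and 84; cohorts of 14.

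**The plan's own figure.** Without clustering, d = 0.50 needs 63 per arm. The design effect is 1 + (7 − 1) × 0.11 = 1.66, and 63 × 1.66 = 104.6, so 105 per arm or 210 in total. The stated 196 does not reproduce with groups of 7. It does with groups of 6: 1 + 5 × 0.11 = 1.55, and 63 × 1.55 = 97.7, so 98 per arm. At 98 per arm in groups of 7, power is 77.5% by the normal approximation and 74.4% by a t-test on 28 group means. That is a separate point; here it shows only that there is no slack.

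**Balance within site.** 112/14 = 8 cohorts and 84/14 = 6 cohorts. One group per arm from each cohort gives 8 + 6 = 14 groups per arm, exactly the stated number. No sentence states the 7/7 split within a site; it is inferred from these figures. The 7 waves of 14 in D.3 make 98 in all, or 98 per site if run at both, and neither matches 112/84. Whole cohorts within a site still follow.

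**Variance.** In SD units, the variance of a group mean is 0.11 + 0.89/7 = 0.237, so the standard error of the arm contrast is √(2 × 0.237/14) = 0.184. Let δ be an assumed site difference in change. With an 8/6 split, omitting site adds δ² × (8 × 6/14)/13 = 0.264δ² to the estimated variance of group means within an arm. The large-sample form, (8/14)(6/14)δ² = 0.245δ², gives 12% in place of 13% in the last row.

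**If δ is additional to rho = 0.11** (complete data; simulated t-test on group means):

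| δ (SD) | Added variance | SE increase | Power without site | Power with site |
|---|---|---|---|---|
| 0 | 0 | 0% | .744 | .742 |
| 0.2 | .011 | 2% | .73 | .74 |
| 0.3 | .024 | 5% | .71 | .74 |
| 0.5 | .066 | 13% | .65 | .74 |

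At δ = 0 the term moves the test from 26 to 25 df and costs about 0.1 point of power. The mean arm estimate is about 0.50 with or without site at every δ.

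**If rho = 0.11 already contains the site variance.** Omitting site keeps power at 77.5% (normal approximation). Including it leaves, at δ = 0.3, a group-mean variance of 0.237 − 0.245 × 0.09 = 0.215 and power of 81.4%. At δ = 0.5 power is 88.4%.

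**Test size.** The plan specifies maximum likelihood in Mplus and names no reference distribution. Suppose an ordinary Wald z with the ML variance (residual sum of squares divided by 28). Rejecting at |z| > 1.96 is the same as |t| > 1.96 × √(26/28) on 26 df, a size of 7.0% with no site difference. With the site term it is |t| > 1.96 × √(25/28) on 25 df, a size of 7.6%. Without the term, size falls to about 5.8% at δ = 0.3 and 4.2% at δ = 0.5. On a t reference it is about 5% with the term, and without it 4.1% at 0.3 and 2.8% at 0.5.

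**The case against.** The strongest reply is that the size of the loss rests on a site difference found nowhere in the documents. The planning correlation was also chosen high: the power section reports 0.07 for the CAPS in the accident pilot and 0.05 in the earlier VA group trial. A site difference of 0.3 SD adds 0.022 of between-group variance (0.245 × 0.09). Added to 0.07 this gives a total correlation of about (0.07 + 0.022)/1.022 = 0.09, still below 0.11. That stands, and it is why both readings of rho are shown.

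Several stronger readings are tempting but unsupported:

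- **Bias.** On the inferred design the arm estimate is unbiased without the term.
- **Baseline severity.** The intercept is centred on pre-treatment and the arm effect is on the slope. A pure site difference in starting severity goes to the intercept; only a site difference in change matters.
- **A test that always runs below 5%.** This holds for a t-test on group means. Under an ML Wald z the unadjusted test exceeds 5% for small site differences, and adding site alone raises it slightly. The power loss appears under both tests (at 0.3 SD with Wald z, .77 against .80), though part of that gap reflects the larger size.
- **A promise of site-adjusted results.** The stress on cross-site consistency in D.3 concerns therapist delivery and is met there by training and supervision. It is not a commitment about the arm estimate.
- **Hypothesis 3.** Its analyses are limited to men with a given comorbidity, so 7/7 balance is not guaranteed. Chance site imbalance is a further reason to adjust there, but the balanced-design figures do not carry over.

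**Conclusion.** The point holds as one of efficiency. The plan pools two sites and tests the arm effect in Hypotheses 1, 3 and 4 with treatment condition as the only named between-level predictor. Any site difference in change therefore enlarges the error of that contrast. The cost ranges from nothing, through about 3 points of power at 0.3 SD, to about 9 points at 0.5 SD if site variance is additional to 0.11. If 0.11 already includes it, nothing planned is lost and the term is a gain.

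These figures assume the inferred within-site balance, complete data and an analysis of group means; the exact values under the Mplus model may differ. The direction does not depend on which reading of rho is taken. The asymmetry favours adjustment: about 0.1 point of power if the sites do not differ, against several points if they do. The documents do not support a charge of bias, nor a general claim that the test is conservative.

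**What to change.** In the Hypothesis 1 text of D.7.a, add the site dummy already planned for Hypothesis 2 as a between-level predictor of both intercept and slope, alongside treatment condition. State that Hypotheses 3 and 4 carry it too, and that it stays in whatever the pre-treatment comparisons show. Keep it in Hypotheses 2 and 5.

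Name the reference distribution for the arm test. With 28 groups, use a small-sample reference (t on about 25 df) so that adding the term does not push the size of an ML Wald test from about 7.0% to 7.6%.

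Report the arm difference by site descriptively. A formal condition-by-site test would have little power: its standard error is about √(2 × 0.237/8 + 2 × 0.237/6) = 0.37 SD. A random effect for the 14-man cohort is not needed; it would add a level with only 14 units of two groups each.

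The cost is one between-level parameter (26 to 25 df) and a few lines of analysis wording. No new data are needed.
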